## 5. STUDY DESIGN AND TREATMENT

### 5.1. Study Design

This is a multicentre, basket, two stage, adaptive single arm Phase II study to examine the efficacy of Debio 1347 administered at the recommended Phase II dose of 80 mg in subjects with solid tumors harboring FGFR1-3 gene fusion/rearrangement. The study will include 3 cohorts of subjects comprising biliary tract cancer (Cohort 1), urothelial cancer (Cohort 2) and, in Cohort 3, all other solid tumor histologies not included in Cohorts 1-2, such as non small cell lung cancer (NSCLC), head and neck cancer, thyroid cancer, oral cancer, breast cancer, prostate cancer and others but excluding primary brain tumors.

Stage 1 will require 27 evaluable subjects across the three cohorts assuming an equal accrual rate per cohort. Stage 2 will require 86 evaluable subjects across all cohorts or per individual cohort depending on results of assessments scheduled at the end of Stage 1 (see graphical algorithm below and Section 11). Assuming a drop out rate of 10%, up to 125 subjects will be enrolled into the study.

Subjects will be treated with Debio 1347 daily in 28-day cycles until the occurrence of disease progression (clinical or radiologic) or unacceptable toxicity (other treatment discontinuation criteria are described in Section 8.4.1). Subject safety (AEs) and survival will be followed-up respectively for 30 days after the last Debio 1347 dose and every 12 weeks from treatment end until death or loss to follow-up but no longer than for a total of 2 years after the last subject has discontinued treatment. Disease status will be followed-up every 12 weeks only in subjects without PD from treatment end until PD, death or loss to follow-up but no longer than for a total of 2 years after the last subject has discontinued treatment.

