### **8.4.2. End-of-study Criteria**

1. Withdraws consent.
2. Adverse event, e.g. intercurrent illness that would, in the judgment of the Investigator, affect assessments of clinical status to a significant degree; or intercurrent illness that, in the opinion of the Investigator or the study Medical Monitor, compromises the subject's safety.
3. Subject non-compliance.
4. Subject lost to follow-up.
5. If, in the Investigator's opinion, continuation in the trial would be detrimental to the subject's wellbeing.
6. A major protocol violation occurs. If a minor protocol violation occurs, the Sponsor's Trial Manager will be contacted to discuss if the subject has to be withdrawn.
7. Prohibited medication as indicated in Section 7.7.3 is required/used during the course of the trial. In the event a subject is found to be taking a prohibited medication during the trial, the site should immediately contact the Medical Monitor. The decision to withdraw the subject will be made in conjunction with the Sponsor.
8. Non-drug related reason; e.g. subject relocates too far from study centre.
9. Sponsor or IEC decides to terminate the study.

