#### **11.5.6.2. Secondary efficacy endpoints**

Disease control rate is defined as the proportion of subjects with a BOR of CR, PR or SD. Disease control rate will be summarized by cohort and overall using frequencies and percentages. The 95% clopper Pearson CI will be presented overall and by cohort.

Duration of response is defined as the time from the date of the first documented PR or CR to date of the first documented disease progression or death due to any cause, whichever occurs first. It will be calculated only for subject with a best overall response of CR or PR.

Progression-free survival is defined as the time from the start date of treatment to date of the first documented disease progression or death due to any cause, whichever occurs first. It will be expressed in months.

The following censoring rules will be applied on PFS and DOR for subject with no documented disease progression or death:

- Subjects who do not experience death or PD, nor initiate a new anti-cancer therapy will be right-censored at the date of their last adequate tumor assessment (i.e. a tumor assessment not showing NE).
- Subjects having initiated a new anti-cancer therapy before experiencing death or PD will be right-censored at the date of their last adequate tumor assessment prior to initiation of a new anti-cancer therapy.
- Subjects who experienced death or PD after two or more consecutive missing or inadequate tumor assessments will be right-censored at their latest adequate assessment before death or PD.

Overall survival is defined as the time from the start date of treatment to date of death due to any cause. Subjects with no documented death will be censored at the last date known to be alive.

Duration of response, PFS and OS will be summarized using the Kaplan Meier method. Median survival time and the associated CI will be estimated. Duration of response rate and PFS rate at 6 month and 1 year, and OS rate at 1 year and 2 years and the corresponding CIs will be estimated using the Kaplan Meier method.

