The interim analysis was not conducted as planned (as detailed in section 10.8.2). Based on an initial statistical review of pooled data, the antitumor activity for Debio 1347 is lower than initially assumed at the time the protocol was developed. Debiopharm decided to permanently halt the enrollment in stage 1 of the study after consultation with the IDMC on June 10th, 2020.

The subsequent protocol amendment 2 (PA2) was implemented to modify the study design in the following ways:

- All ongoing patients (on-treatment subjects and off-treatment subjects still under follow-up) will be re-consented to PA2.
- Subjects showing clinical benefit may remain on-treatment with Debio 1347 until a condition to stop treatment is met.

- After consenting to PA2, on-treatment subjects will no longer be assessed for efficacy in the study, but only for AE, SAE and AESI as described in the pared down study plan of PA2 (**Error! Reference source not found.**).
- Off-treatment subjects will not be followed for disease status or survival in the study, but only for AE, SAE and AESI up to 30 days after the last dose of Debio 1347.
- Subjects will complete study participation at 30 days after the last dose of Debio 1347. In the case of off-treatment subjects with >30 days and <2 years follow-up at the time of PA2 implementation, then these subjects can end (i.e. complete) study participation immediately.
- Subsequent efficacy data collected through standard institutional care practice in on-treatment and off-treatment subjects will not be collected in the eCRF.
- No further IDMC meetings will be required.

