10.1 Disposition of Subjects, Demographic and Baseline Data

10.1.1 Subject Disposition

Number (%) of patients will be presented by total patients only for All Screened Subjects, in the following:

- Screened (patients with informed consent) (number only)
- Screened but not enrolled and by reason for not enrolling

Number of patients will be presented for:

- Enrolled but not treated
- Treated

Number (% , calculated using denominator of treated patients) will be presented for

- End of treatment status (ongoing at data cut-off, discontinued) and by reason for treatment discontinuation
- End of study status (ongoing at data cut-off, discontinued) with reason for study discontinuation
- Subject in ITT, mITT, Safety, PP, PK population.

Number (%) of patients will be summarized in each analysis population (ITT, mITT, PP, SAF and PKP). Reasons for exclusion from PP will be provided:

- No measurable disease at baseline (inclusion criterion 7)
- No post-baseline disease assessment
- Violation of eligibility criteria at entry
- Treatment compliance <75%
- Other major protocol deviation that potentially affects efficacy assessment

Subjects per country and sites will be tabulated for the ITT, mITT and PP.

All subject disposition data will be presented in data-listings. Screening failure and reasons will be listed separately. Reason of exclusion from each analysis population will be listed.

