10.2 Efficacy Analyses

The efficacy analysis will be performed on the ITT population as the primary analysis. All efficacy analyses will be repeated on the mITT and PP population as supportive analysis, unless otherwise stated.

PA2 shortens the data collection period for efficacy data. Compared to early enrolled subjects, the later enrolled subjects will systematically have less tumor response assessments at PA2 implementation and time to event variables censored at date of last dose. There will be no additional statistical considerations to specifically address these systematic differences between earlier and later enrolled patients, and therefore, the planned statistical methods remain same as before PA2 was implemented.

Also, since the homogeneity assessment at interim analysis was not conducted, the efficacy endpoints will be analyzed and reported by cohort and pooled total subjects.

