10.2.6 Overall Survival

Overall survival (months) is defined as (date of death due to any cause - the start date of treatment +1)/30.4375. Subjects with no documented death will be censored at the last date known to be alive (i.e. latest date collected in the eCRF).

Survival rate at every 6 months will be presented with the corresponding 95% CIs will be estimated using the K-M method. A K-M plot for OS will be presented.

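### SAP 10.2.6 does not limit the last date known alive to dates that show the subject was alive, so OS can be overstated for subjects lost or closed out without contact

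*SAP*

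**What the plan says.** Protocol 11.5.6.2 gives the OS censoring rule without further definition: "Subjects with no documented death will be censored at the last date known to be alive". SAP 10.2.6 repeats the rule and adds a parenthesis: "i.e. latest date collected in the eCRF". It excludes no type of date. The SAP then reports Kaplan-Meier survival rates every 6 months with 95% confidence intervals.

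Other provisions bear on which dates the eCRF may hold:

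- **Survival contact.** Protocol 5.1 plans it "every 12 weeks from treatment end until death or loss to follow-up". Protocol 8.2.7 adds a window of ±14 days and counts the schedule from the last dose.
- **Amendment 2.** Survival follow-up stops (Protocol 8.2.7, SAP 4.1.2). For off-treatment subjects with more than 30 days and less than 2 years of follow-up, SAP 4.1.2 says "then these subjects can end (i.e. complete) study participation immediately". The same list says that all ongoing subjects, including off-treatment subjects still under follow-up, will be re-consented.
- **End of study.** Protocol 8.4.2 includes "Subject lost to follow-up" among the reasons. SAP 10.1.1 tabulates "End of study status (ongoing at data cut-off, discontinued) with reason for study discontinuation".
- **Signature.** Protocol 12.6 requires an investigator to sign and date each eCRF electronically.
- **A different date.** SAP 10.2 describes later-enrolled subjects as having "time to event variables censored at date of last dose".

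**The concern.** The protocol's rule and the SAP's definition agree only when the latest eCRF date is itself evidence of life. When it is administrative, the subject stays in the risk set from the last real contact to the administrative date. If a death in that interval is not recorded, Kaplan-Meier gains time at risk without the event, and the curve rises.

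PFS and duration of response have a safeguard that OS lacks: SAP 10.2.2 and 10.2.5 tie their censoring to the last adequate tumour assessment.

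The trial has a single arm, so no comparator shares and offsets such a bias; the survival rates are read as absolute figures. The cohorts are also small. At the second IDMC meeting there were 63 evaluable subjects, 4 of them urothelial (SAP 10.8.2), so a few misdated subjects could move a cohort curve.

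**Working it through.** **1. Which dates could qualify**

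| eCRF date | Shows the subject alive? | Excluded by SAP 10.2.6? |
|---|---|---|
| Attended visit, sample, scan, ECG, dose taken | Yes | No |
| Survival contact with status alive | Yes | No |
| Signed Amendment 2 re-consent | Yes | No |
| End-of-study or lost-to-follow-up form date, no contact | No | No |
| eCRF signature date | No | No |
| Imputed adverse-event or medication end date | No | Not stated |

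On the last row: SAP 8.1.1 fills a wholly missing adverse-event end date with the end of the on-treatment period, which SAP 9.4 sets at 30 days after last dose, or death if earlier. SAP 8.1.2 fills a missing month in a medication end date with December. Strictly, an imputed date is not a collected one, but the SAP does not rule it out for OS.

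**2. Length of the gap**

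Contacts fall every 84 days, each with ±14 days, anchored to last dose.

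- One interval plus one window: 84 + 14 = 98 days, and 98/30.4375 = 3.22 months. This is the gap used below.
- Widest on-schedule spacing, an early contact followed by a late one: 84 + 14 + 14 = 112 days.
- For a subject already lost, the contact schedule sets no upper limit.

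**3. Illustrative size**

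The documents give no OS median, event count or loss rate, so there is no figure to reproduce and every input here is assumed. Set-up: 40,000 simulated subjects per scenario; exponential OS with median 6 or 12 months; 2-16 months of potential follow-up; a stated share assigned to loss at a uniformly distributed time; administrative date 3.22 months after last contact, capped at close-out; no gap death recorded. Kaplan-Meier was run with the lost subjects censored at last contact and again at the administrative date.

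| True median (months) | Assigned to loss | Median, last contact → administrative | 12-month OS (%), last contact → administrative |
|---|---|---|---|
| 6 | 5% | 5.91 → 6.02 (+0.11) | 24.8 → 25.3 (+0.5) |
| 6 | 10% | 6.06 → 6.26 (+0.20) | 25.0 → 26.2 (+1.2) |
| 6 | 20% | 6.02 → 6.46 (+0.44) | 25.2 → 27.8 (+2.6) |
| 12 | 5% | 12.16 → 12.31 (+0.15) | 50.4 → 50.9 (+0.5) |
| 12 | 10% | 11.99 → 12.43 (+0.44) | 50.0 → 51.1 (+1.1) |
| 12 | 20% | 12.06 → 12.76 (+0.70) | 50.2 → 52.5 (+2.3) |

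Over the wider grid (5-40% loss; gaps of 1, 3.22 and 6 months) the shift was upward in all 24 scenarios. It ran from +0.2 points and +0.03 to +0.07 months (5%, 1 month) to +7.7 to +9.3 points and +1.4 to +3.2 months (40%, 6 months). With no such subjects it is zero.

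**4. Dependence on recording of gap deaths**

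A separate stress case closes every survivor without contact at 1-16 months, with 12-week contacts. True 12-month OS is 0.250, 0.397 and 0.500 for medians of 6, 9 and 12 months.

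| Gap deaths recorded | Censored at administrative date | Censored at last contact |
|---|---|---|
| 50% | 0.283 / 0.432 / 0.532 | 0.217 / 0.361 / 0.464 |
| 100% | 0.250 / 0.398 / 0.501 | 0.189 / 0.327 / 0.431 |

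At 50% the two rules miss by similar amounts in opposite directions: +3.2 to +3.5 points against -3.3 to -3.6. At 100% the administrative date is essentially unbiased and last contact is low by 6.1 to 7.0 points. With none recorded, the administrative date is biased upward.

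**The case against.** The case on the other side has four parts.

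- **The wording can be read narrowly.** The operative phrase is still the protocol's, and the parenthesis may only name the data source. No document shows an end-of-study or lost-to-follow-up date field, or says that such a date is used. This stands against claiming that OS will be overstated. It does not remove the ambiguity, because the parenthesis is worded as a definition and has no exclusions.
- **Re-consent supplies a valid date.** A reader might infer that everyone off treatment at Amendment 2 is closed on an administrative date after an unseen death. SAP 4.1.2 does not support that. It plans re-consent of off-treatment subjects still under follow-up, a signed re-consent is evidence of life, and seeking it would tend to reveal deaths. Subjects already lost are not helped. The protocol's post-amendment study plan does not settle the point, since it covers only subjects still on treatment.
- **Upward bias is not automatic.** It requires that gap deaths go largely unrecorded, and deaths are to be listed (Protocol 11.5.7, SAP 10.3.2). That is correct and limits the claim. But after Amendment 2 off-treatment safety follow-up ends 30 days after last dose and survival is no longer followed, so later deaths are not actively sought.
- **The consequence is limited.** OS is secondary, with no test or decision rule, and enrolment was halted on response data. That stands.

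**Conclusion.** The point holds as a defect in the rule, not as a demonstrated error in the result. SAP 10.2.6 allows a censoring date later than any evidence of life, which the protocol's rule does not. OS can therefore be overstated, mainly for subjects lost to follow-up or closed at Amendment 2 without contact or re-consent.

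The documents give neither the eCRF date fields nor the number of subjects affected, so the size in this trial is unknown. The 0.5-2.6 points at 12 months and 0.1-0.7 months in the median rest on 5-20% assigned to loss, a 3.22-month gap, exponential survival and no recorded gap deaths. The bias shrinks as more gap deaths are recorded and is absent where the latest date is a real contact.

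The change should be made because it is cheap and restores the protocol's rule. It does not alter the primary analysis.

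**What to change.** In SAP 10.2.6, delete the parenthesis and define the last date known alive as the latest of: attended visit; dose taken; sample, scan or other assessment performed; survival contact with status alive; signed re-consent. Exclude end-of-study and lost-to-follow-up dates without documented contact, imputed dates, and data-entry or signature dates.

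Reconcile this with SAP 10.2, whose reference to the date of last dose gives a programmer a second, conflicting censoring date for OS.

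The change has one drawback. If some deaths after last contact are recorded while survivors are censored at last contact, OS can be biased downward. Step 4 shows this at its most extreme; with few subjects affected it is small. Report the number of subjects, by cohort and overall, whose last alive date precedes their end-of-study date, so that a reader can judge the exposure under either rule.

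The cost is a revised SAP sentence, a source list in the OS programming specification and one count in the output. No new data are needed.

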10.2.7 Subgroup Analysis

ORR and DOR analysis will be repeated, whenever appropriate, on the following subgroups:

- By gender (Male, Female)
- By Region: North America, Europe, Rest of the world
- Subjects with a dose-reduction (as per investigator's decision)
- Subjects with no dose-reduction (as per investigator's decision)

However, given the early stopping and reduced data collection after PA2, it is deemed not appropriate to perform the subgroup analysis.

10.3 Safety Analyses

The safety analysis will be conducted in the Safety Population.

After PA2 is in force, safety assessments for on-treatment and off-treatment subjects will be performed using standard institutional practice and using local laboratory testing. Generally, safety data collected by the local investigator at all clinic visits but only AEs, SAE and AESI will be recorded in the eCRF to support the ongoing safety assessments up to 30 days after last administration of study treatment. The changes in study design relating to safety data include:

- Central clinical laboratory will no longer be performed but will use the local laboratory. Central and local laboratory data will be analyzed together, i.e. not separate analysis for each data source. Shifts in central and local laboratory values will be determined based on the central or local reference range, respectively.
- ECGs will not necessarily be collected in triplicate and central reading will not be performed. Local reading of ECGs will be used. Central and local ECG readings will be analyzed together.

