**Safety analysis**

*AEs*: Treatment-emergent adverse events, TEAEs related to study drug, TEAEs by severity, TEAEs leading to treatment discontinuation and SAEs will be tabulated and listed by MedDRA system organ class and preferred term. All on study deaths and reasons will be listed.

*Laboratory parameters*: Safety laboratory parameters and corresponding changes from baseline will be presented as descriptive statistics by cohort and by timepoint. Shift tables will be produced.

*ECGs*: 12-lead ECG parameters and corresponding changes from baseline will be summarized by cohort and by visit as descriptive statistics. No central reading of the original ECGs will be performed. Central tendency, categorical and morphological analyses will be performed for all available parameters. Subordinated to the safety and efficacy outcome and data availability, an exposure-response (C-QTcF) analysis may be performed by linear mixed effect modeling based on ECG and PK matching time-points, if deemed appropriate.

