10.3.4 Vital Signs

Vital signs parameters include:

- weight (kg)
- systolic blood pressure (mmHg)
- diastolic blood pressure (mmHg)
- heart rate (beats/min)

Actual values and corresponding changes from baseline will be summarized by visit as descriptive statistics.

All vital signs data will be presented in a by-subject listing.

10.3.5 12-lead ECG

All ECGs will be sent to a local and central cardiology laboratory for reading and analysis. ECG measurement will include:

- RR, defined as the interval between 2 consecutive R waves (ms);
- Heart rate (HR, in beat per minute [bpm]), calculated as $60000 / RR$ (ms);
- P-R, defined as the interval between P and R waves (ms);
- QRS, defined as the distance between the Q and the S waves (ms);
- QT, defined as the interval between Q and T waves (ms);
- $QTcF$ (ms) = QT (ms) / RR (s)^{1/3}.

The triplicate values will be averaged in order to obtain one single value per subject and time point.

As per Protocol Amendment N° 2, central ECG reading will not be performed.

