10.3.5.1 Central Tendency Analysis

Actual values for central assessment ECG parameters and their changes from baseline will be summarized using the descriptive statistics by time point. Ninety percent CIs of the mean will be presented as well. Standard deviation will be computed only if at least 3 records are available and 90% CIs only for cohorts in which at least 6 subjects are available.

Graphical representation of mean changes from baseline (with their 90% CIs upper bound when applicable) over time will be provided.

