10.3.5.2 Categorical Analysis

The number and percentage of subjects presenting at least one value above the thresholds (irrespective of the cycle or time point) as defined in Table 3 will be computed per cohort and overall. All ECG collected (including unscheduled assessments) will be used for this analysis.

Table 3 - Thresholds for categorical analysis and corresponding flags for listings

Criteria	Flag
Actual values	
P-R > 220 ms	H
QRS > 120 ms	H
QTcF interval > 450 ms	B

QTcF interval > 480 ms	H
QTcF interval > 500 ms	P
Changes from baseline	
P-R relative change > 25%	I
QRS relative changes > 25%	I
QTcF interval increase from baseline > 30 ms	I
QTcF interval increase from baseline > 60 ms	I+

Flagging system will be used in listings to identify values above thresholds, also not necessarily related to clinically significant events, the flags can be interpreted as follows:

- B: Borderline value;
- H: High value;
- P: Prolonged value;
- I: Noticeable absolute increase from baseline;
- I+: Marked absolute increase from baseline.

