10.6 C-QTcF analysis

If deemed appropriate depending on the safety and efficacy outcomes and data availability, an exposure-response (C-QTcF) analysis may be performed as described below.

Concentration-response relationship will be investigated for change from baseline in QTcF from central reading and Debio 1347 plasma concentrations.

This study did not include a placebo control and no run-in period with ECG recording before dosing with study drug. Therefore, placebo effects on QTcF could not be evaluated and accounted for.

10.6.1 Graphical Exploration:

In order to assess quality of QTcF correction before and after dosing the following figures will be provided:

- Scatter plot of QTcF versus RR at baseline with a regression line.
- Scatter plot of change from baseline for QTcF versus change from baseline in RR for values collected during Debio 1347 treatment periods with a regression line.

In both cases, the regression lines should tend toward a horizontal line, otherwise, a dependency still exists between QTcF and RR and a study specific QT correction (QTcSS) may be considered as the preferred dependent variable.

The following exploratory plots will also be performed before starting the modelling:

- Scatterplot of individual change from baseline for QTc values vs. time-matched concentrations including a nonparametric trend curve will be provided to assess the pattern of the relationship.
- Scatterplot of individual change from baseline for HR values vs. time-matched concentrations including a nonparametric trend curve will be provided to detect impact of the treatment on HR.

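### The categorical QTcF table can subtract a baseline read by one source from a value read by another, and the documents conflict on which ECG readings each analysis uses

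*SAP*

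**What the plan says.** SAP 10.3 describes what Amendment 2 changes for ECGs: "ECGs will not necessarily be collected in triplicate and central reading will not be performed". Local reading is used instead, and "Central and local ECG readings will be analyzed together".

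SAP 10.3.5 (12-lead ECG) states that "All ECGs will be sent to a local and central cardiology laboratory for reading and analysis". It adds that "The triplicate values will be averaged in order to obtain one single value per subject and time point", and closes by noting that central reading stops under Amendment 2.

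The analyses name different sources:
- **Central tendency (SAP 10.3.5.1):** "Actual values for central assessment ECG parameters and their changes from baseline will be summarized".
- **Categorical (SAP 10.3.5.2):** a subject counts with at least one value above a threshold, at any cycle or time point. "All ECG collected (including unscheduled assessments) will be used for this analysis". Table 3 of the SAP includes QTcF increases above 30 ms and above 60 ms.
- **C-QTcF (SAP 10.6), if performed:** "Concentration-response relationship will be investigated for change from baseline in QTcF from central reading".

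The protocol synopsis, under Safety analysis, says: "No central reading of the original ECGs will be performed".

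SAP 9.1 defines baseline as the latest value before study drug and does not mention the reader.

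**The concern.** A change from baseline is a difference of two readings. If one is central and the other local, any systematic difference between readers goes straight into the change. If the later value is a single tracing and the baseline a mean of three, the change is also noisier. A table that counts subjects with at least one exceedance responds to both. A positive local-minus-central offset adds subjects to the count without a drug effect, and a negative one can hide a real increase.

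The SAP deals with source for laboratory data in the same list: shifts are judged against the central or the local reference range as applicable. The ECG item has no equivalent rule.

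The QTcF counts matter because the protocol (3.3.2) describes the Phase I exposure-response analysis as not fully conclusive on QTcF prolongation. The conflicting statements on central reading also leave a programmer to choose the source, possibly after seeing the data.

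**Working it through.** **Step 1. Which analysis uses which source?**

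| Place | Source stated | Can a change mix readers? |
|---|---|---|
| SAP 10.3 | Central and local together | Yes, if applied generally |
| SAP 10.3.5 | Local and central, then no central under Amendment 2 | Two readings of one tracing are possible |
| SAP 10.3.5.1 | Central | No, as written |
| SAP 10.3.5.2 | All ECGs collected | Yes |
| SAP 10.6 | Central | No, as written |
| Protocol synopsis, Safety analysis | No central reading | No, if literal |

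The gap as written is therefore in the categorical change rows.

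**Step 2. Do central readings exist?** Protocol Table 8-1, footnote c, sends all ECGs to a central cardiology laboratory. Protocol 8.2.3 says Amendment 2 ends central reading. There are two possible readings:
- The synopsis sentence means only that central reading stops with Amendment 2. Then earlier central readings exist, and mixing in the categorical table is possible.
- The synopsis sentence is literal. Then nothing is mixed, but SAP 10.3.5.1 and 10.6 have no data and cannot be run as written.

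Either way the text needs a correction.

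**Step 3. How large could the effect be?** The plan has no figure to reproduce, and the documents give no QTcF SD or reader offset. The following inputs are assumptions, for scale only:
- visit-to-visit SD sv = 8 or 12 ms
- replicate SD sr = 5 or 8 ms
- local-minus-central offset b = 0 or ±10 ms
- no drug effect, and a triplicate baseline

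The change is taken as normal with mean b and variance 2·sv² + sr²/3 + sr²/m, where m = 3 for a triplicate later value and m = 1 for a single tracing. The chance of exceeding 30 ms is P(Z > (30 − b)/SD).

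Worked example, sv = 12, sr = 8, m = 1: variance = 288 + 21.33 + 64 = 373.33, so SD = 19.32 ms. With b = 0, z = 30/19.32 = 1.55 and the chance is 6.03%. With b = +10, z = 20/19.32 = 1.04 and it is 15.03%. With b = −10, z = 40/19.32 = 2.07 and it is 1.92%.

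Chance (%) that one change exceeds 30 ms:

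| sv / sr (ms) | Triplicate, b = 0 | Single, b = 0 | Single, b = +10 | Single, b = −10 |
|---|---|---|---|---|
| 8 / 5 | 0.63 | 0.91 | 5.77 | 0.08 |
| 8 / 8 | 1.08 | 2.00 | 8.55 | 0.31 |
| 12 / 5 | 4.28 | 4.71 | 13.23 | 1.28 |
| 12 / 8 | 4.95 | 6.03 | 15.03 | 1.92 |

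Moving from triplicate to single adds about 0.3 to 1.1 percentage points. The offset does most of the work, in either direction. The chance of exceeding 60 ms is at most 0.48% in any of these settings.

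**Step 4. Does this reach the 20 ms rule?** SAP 10.6.4 applies the 20 ms limit to the C-QTcF model, which SAP 10.6 specifies on central readings. The model needs ECG-PK pairs, and PK sampling with matched ECGs is scheduled only on Day 28 of Cycles 1 and 2 (Protocol 8.2.5). If the last subject started on 10 June 2020, the date of the decision to halt enrolment (an assumption), Cycle 2 Day 28 would be 4 August 2020. The protocol version for Amendment 2 is dated 16 July 2020, so only the latest subjects could have a pair after that date. As written, pooling does not enter the rule.

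**The case against.** **The table is a deliberately inclusive safety screen.** Using every ECG, including unscheduled ones, avoids losing a signal. This stands, and it is a good reason not to restrict the table to central readings. It does not justify subtracting one reader's baseline from another reader's later value.

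**Few late local values may reach the database.** SAP 10.3 itself says that after Amendment 2 only AEs, SAEs and AESIs go into the eCRF. This stands too: the number of affected changes is unknown and may be small. It does not settle which reading counts for tracings read by both sources before Amendment 2.

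**Specific rules override the general one.** SAP 10.3.5.1 and 10.6 can be read as exceptions to the pooling sentence. That is reasonable, but the SAP does not say so, and SAP 10.3.5.2 has no such exception.

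A reader might also infer two stronger points that the documents do not support:
- *That the worse of two readings is the one counted.* A literal at-least-one rule could have that effect if both readings are kept as records, but no sentence directs it. SAP 10.3.5 asks for one value per subject and time point, without saying from which reader.
- *That baseline is always a centrally read triplicate mean.* SAP 9.1 names no reader, and SAP 10.3.5 has both readers before Amendment 2.

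**Conclusion.** The point holds for the categorical change-from-baseline rows in SAP 10.3.5.2 and for the conflicting statements on reading source. The pooling sentence, the at-least-one count and a baseline definition that is silent on the reader together allow reader differences to inflate or mask the counts. The effect falls mainly on the 30 ms row. Its size depends on a reader offset that the documents do not give, and on how many local values are in the database. The percentages above rest on assumed SDs and offsets and show scale only.

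A reader might infer that pooling also compromises the exposure-response objective for QTcF. For example, the Phase I upper bound of 11.44 ms at 80 mg leaves 20 − 11.44 = 8.56 ms to the limit, and a reader offset could be set against that margin. The documents do not support this: the mean-change and C-QTcF analyses are specified on central readings, and the C-QTcF analysis is itself conditional. That would change only if the pooling sentence were taken to override SAP 10.3.5.1 and 10.6, which is one more reason to reconcile them.

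This is a cheap improvement to a descriptive safety table.

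**What to change.** In SAP 10.3 and 10.3.5.2:
- Compute each change from baseline within one reading source: central minus central, or local minus local.
- Where a tracing has both readings, use the central one.
- Keep all ECGs in the categorical counts, including local-only and unscheduled ones. Flag each by source and as single or triplicate, and show the counts by source.

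Reconcile the protocol synopsis (Safety analysis) with SAP 10.3, 10.3.5, 10.3.5.1 and 10.6. State which source each analysis uses, and that 10.3.5.1 and 10.6 use central readings obtained before Amendment 2, if these exist.

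Cost: SAP wording, one source flag and a few more table rows, with no new data. A local later value without a local baseline becomes not evaluable for the change rows. It still counts in the absolute-value rows, which need no baseline.
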